8.2.1. Inclusion Criteria

Two cohorts will be produced. First, a CPRD cohort, using linked primary care, medication, Hospital Episode Statistics, and socio-economic data, according to the following inclusion criteria:

- 1. Diagnosis of COPD before index date (time period will be defined in the SAP)
- 2. Aged ≥40 at index date.
- 3. Alive, and registered with a GP, at index date.
- 4. Not registered with a GP in the Greater Manchester area.

Second, a Salford cohort will be constructed using the Salford Integrated Record (SIR), according to the inclusion criteria:

- 1. Diagnosis of COPD before index date.
- 2. Aged ≥40 at index date.

WWEpi Project number: PRJ2282

3. Alive, and registered with a GP, at index date.

Restricted cohorts will then be constructed in both the Salford and CPRD populations, based on the inclusion/exclusion criteria and study period for the SLS:

- Patients with documented GP diagnosis of COPD, and currently receiving maintenance therapy
- 2. Male or female subjects aged ≥40 years of age at index date
- 3. Patients who have a history of treatment with systemic/oral corticosteroids, antibiotics (in association with GP contact) and/or hospitalisation for at least one COPD exacerbation in the 3 years prior to index date.
- 4. Current COPD Therapy

All patients currently receiving either:

- inhaled corticosteroid (ICS) alone or in combination with a long acting bronchodilator (this could be a fixed dose combination or an ICS/LABA provided in two separate inhalers, or ICS and LAMA),
- or long-acting bronchodilator therapy alone (e.g. tiotropium or salmeterol, or the use of two bronchodilators i.e. LABA/LAMA),
- or "triple therapy" i.e. ICS/LABA plus a Long Acting Muscarinic Antagonist (LAMA)

Finally, the third data source, the SLS, will be used as-is.

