8.3.3. Confounders and effect modifiers

- Sex
- Age
- Socio-economic status (SES)
- Current/SOC COPD Medication group:

WWEpi Project number: PRJ2282

- LAMA or LABA only
- o LAMA+LABA
- LABA+ICS (combination product or two inhalers)
- o LABA+ICS+LAMA
- Comorbidities
 - Cardio-and cerebrovascular diseases (heart failure, myocardial infarction, stroke)
 - o Depression
 - o Anxiety
 - o Asthma
 - History of pneumonia
 - Gastro-oesophageal reflux and peptic ulcer disease
 - o Diabetes
 - Charlson score (COPD will be removed from score)
- Markers of COPD severity
 - o Previous COPD exacerbation
 - FEV1 % predicted
 - FEV1/FVC ratio
 - GOLD stage
 - MRC Dyspnoea score
- Comedications: major medication classes for each comorbidity of interest
- Smoking
- BMI
- Vaccinations
- Disability status

Further information on the definitions for the variables above will be provided in the SAP.

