Firstly, for descriptive purposes, we will measure the prevalence of the endpoints in a series of subgroups. For example, we will compare the COPD exacerbations in CPRD-xGM-IC with SLS, stratified by SES, gender, etc.

Secondly, we will take a multilevel modelling approach. For this we will combine the SLS and CPRD into one dataset (retaining an indicator of SLS membership). The hierarchies of the model will be patient -> GP practice -> local authority region (with SLS members being treated as a single distinct region) -> strategic health authority region. Strategic health authorities (population threshold of 1 million) are non-anonymised (named) regions. Local authority regions are below the population threshold so an anonymised LA marker will be available.

We will include all confounders and effect modifiers as covariates, with outcomes corresponding to the primary and secondary study outcomes (a separate model for each). Important fixed effects at the local authority level (for example, existence of community teams) will be incorporated into the model if these can be ascertained.

A final model will be selected via backward selection using AIC (Akaike Information Criterion). We will then examine the random effect of the SLS region in the context of the random effects for the other regions. Similar to the above, if the random effect of the SLS region falls outside the 2.5-97.5 percentile range, we will conclude that SOC SLS behaves unusually compared with the rest of the UK, and hence evidence of a Hawthorne effect.

PO3 will be carried out using the same approach as for PO2.

SO1 and SO2 (which pertain to comparing other endpoints, and sensitivity analyses of endpoint definition) will be carried out in the same way as PO2.

SO3 makes explicit the possible change in outcomes at commencement of SLS. We will compare outcome rates within Salford before and after the commencement of SLS, in a self-controlling case design. We will do the same thing within CPRD to control for UK-wide secular trends. This acts as sensitivity analysis to support PO2 (using controls distinct in time rather than in geography).

WWEpi Project number: PRJ2282

Additional work will take place exploring the development of methods for a framework of measuring representativeness; this is not within scope of this protocol and is described in Annex 2.1.

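### AIC backward selection can override the pre-specified confounder set, which weakens adjustment for rarer outcomes such as serious pneumonia; separately, the medication covariate has no level for two eligible therapy classes

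*Protocol*

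**What the plan says.** Section 8.7.1 of the protocol describes the PO2 model in two steps. First, the starting set is complete and there is one model per outcome: "We will include all confounders and effect modifiers as covariates, with outcomes corresponding to the primary and secondary study outcomes (a separate model for each"). Second, that set is reduced: "A final model will be selected via backward selection using AIC (Akaike Information Criterion"). The text protects no covariate from removal.

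The conclusion comes from the reduced model: "if the random effect of the SLS region falls outside the 2.5-97.5 percentile range, we will conclude that SOC SLS behaves unusually". The approach carries over to the other co-primary outcome, "PO3 will be carried out using the same approach as for PO2", and SO1 and SO2 "will be carried out in the same way as PO2".

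Section 8.3.3 lists the confounders, including a medication group with four levels, and leaves further variable definitions to the SAP. The only level that pairs ICS with a single bronchodilator is "LABA+ICS (combination product or two inhalers"). Section 8.2.1, item 4, is wider. It accepts ICS used alone, and its list of combinations runs to ICS/LABA "provided in two separate inhalers, or ICS and LAMA").

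**The concern.** The 8.3.3 variables are listed because SLS and CPRD patients may differ on them. Whether a variable confounds depends on its association with the outcome and on its imbalance between the two sources. AIC sees only the first. A confounder that is clearly unbalanced but has a modest effect can be deleted simply because the outcome has few events. Since selection runs outcome by outcome, the adjustment sets can also differ, and the SLS effects would then not be comparable across outcomes. What is dropped remains in the SLS term, which the protocol reads as unusual behaviour of the SLS region.

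The medication gap is a separate matter. Patients who are eligible under 8.2.1 but fit no level in 8.3.3 could end up unclassified, excluded from the adjusted models or placed in the wrong group. The PO1 tables are affected too, because 8.7.1 tabulates the 8.3.3 list.

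**Working it through.** The protocol gives no event rate, power or effect size for this step, so there is no figure of its own to reproduce.

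**1. What AIC drops.** AIC = -2 log L + 2k. Removing a term with q degrees of freedom lowers AIC when its likelihood-ratio chi-square is below 2q.
- q = 1: P(chi-square > 2) = 0.157
- q = 3 (the four-level medication group): P(chi-square > 6) = 0.112
- q = 5 (the same group with two levels added): P(chi-square > 10) = 0.075

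A term with a p-value above its threshold is dropped. SLS-CPRD imbalance does not enter the criterion.

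**2. Analytic size, rarer outcomes.** Assumed: 300-1,000 events; binary confounders with 20% prevalence and log effect b of 0.08-0.18; each 10 percentage points more common in SLS.
- Mean z = b × sqrt(events × 0.2 × 0.8)
- Drop probability = P(|Z| < sqrt 2)
- Shortfall = b minus the expected value of the estimate counted as zero when dropped
- Bias = number of confounders × 0.10 × shortfall

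Example: 616 events, b = 0.12. Mean z = 0.12 × sqrt(98.56) = 1.19; drop probability 58%; shortfall 0.032. Ten confounders give 10 × 0.10 × 0.032 = 0.032 and twenty give 0.064 on the log scale. Over the assumed range the drop probability runs from 19% (1,000 events, b = 0.18) to 78% (300 events, b = 0.08). The bias is about 1-5% for ten confounders and 3-9% for twenty.

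**3. Chance of keeping a weak confounder (log rate 0.05 per SD).** From 8.5: SLS target 2,800 in total, CPRD at least 2,800 and expected to be 5-10 times larger. Assumed: SOC arm 1,400, and the event rates shown. Mean z = 0.05 × sqrt(total events).

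| Outcome, CPRD size | Total events | P(kept) |
|---|---|---|
| Exacerbation 1.0/yr, 14,000 | 15,400 | 1.00 |
| Exacerbation 1.0/yr, 2,800 | 4,200 | 0.97 |
| Pneumonia 0.03-0.06/yr, 14,000 | 462-924 | 0.37-0.54 |
| Pneumonia 0.03-0.06/yr, 2,800 | 126-252 | 0.22-0.28 |

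**4. Simulation with a true SLS log rate ratio of 0.** Assumed: 1,400 SOC patients; 20 independent confounders, all shifted 0.2 SD in the same direction; log rate per SD 0.08 (pneumonia, 0.04/yr) or 0.05 (exacerbation, 1.0/yr). These imply crude bias of 20 × 0.08 × 0.2 = 0.32 and 20 × 0.05 × 0.2 = 0.20, which the crude column matches. The models were single-level Poisson, with Wald z-squared below 2 standing in for AIC.

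| Outcome, CPRD size | Crude | AIC | Full | Kept | SD, AIC v full |
|---|---|---|---|---|---|
| Pneumonia, 2,800 | 0.323 | 0.101 | 0.008 | 37% | 0.168 v 0.169 |
| Pneumonia, 14,000 | 0.322 | 0.033 | -0.003 | 72% | 0.105 v 0.105 |
| Exacerbation, 14,000 | 0.201 | 0.003 | 0.003 | 100% | 0.022 v 0.022 |

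For pneumonia, selection left 0.101/0.323 = 31% and 0.033/0.322 = 10% of the crude confounding. The runs were small (150, 60 and 40 replicates). The Monte Carlo standard errors of the AIC means are 0.168/sqrt(150) = 0.014, 0.105/sqrt(60) = 0.014 and 0.022/sqrt(40) = 0.003, so the means are approximate.

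**5. Medication classes side by side.**

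| Eligible under 8.2.1 | Level in 8.3.3 |
|---|---|
| ICS alone | none |
| ICS + LABA | yes |
| ICS + LAMA | none |
| One long-acting bronchodilator | yes |
| LABA + LAMA | yes |
| ICS + LABA + LAMA | yes |

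**The case against.** The strongest reply is that the harm is small where it would matter most. The objectives tie detection of a Hawthorne effect to PO2, not PO3. For PO2 at the expected CPRD size the simulation kept every confounder, and the AIC estimate equalled the fully adjusted one. That stands. A reader might infer from 8.7.1 that confounding control is lost, or that the PO2 verdict is compromised; neither is supported. AIC can remove confounders but need not, and for frequent events it rarely would.

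The magnitudes also lean towards the unfavourable side. The confounders are independent and all unbalanced in one direction, so a retained variable cannot stand in for a dropped correlated one. Restricting CPRD to SLS eligibility should reduce imbalance. This stands as a limit on size. It does not justify the selection step, which gained no useful precision in any scenario.

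Nor is an effect on the decision rule shown. The rule compares the SLS random effect with the spread of the region effects, which the documents do not give. A bias of 0.01-0.05 is less than half the pneumonia sampling SD of 0.105-0.169; the 0.101 found at the CPRD minimum is 0.101/0.168 = 0.6 of it. A reader might also object that confidence intervals ignore the selection, but 8.7.1 specifies no interval for the SLS effect.

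The stratified comparisons and the before-and-after analysis (SO3) are not stated to use AIC and give other evidence. They do not repair the modelled PO3 result.

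On medication, 8.3.3 leaves further definitions to the SAP. Defining the listed levels does not create the two missing ones, so the conflict with 8.2.1 remains. That patients would actually be dropped or misfiled is an inference, since no handling rule is stated.

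**Conclusion.** The point holds in a limited form. Section 8.7.1 lets a criterion blind to SLS-CPRD imbalance override the pre-specified adjustment set, separately for each outcome. Adjustment is weakened rather than lost. For PO2 the effect is negligible at the expected CPRD size; PO2 bias at the 2,800 minimum was not simulated, although a confounder of 0.05 per SD would still be kept 97% of the time. For serious pneumonia, a co-primary outcome, and for other rare outcomes such as deaths, residual confounding of roughly 1-10% in the SLS effect is plausible. The upper end belongs to a CPRD cohort near 2,800.

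These sizes rest on assumed SOC arm size, event rates, effects and aligned imbalances, and on single-level models with a group term rather than the planned multilevel model with a regional random effect. Whether a shift of this size would change a conclusion cannot be judged from the documents.

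The medication gap is a plain inconsistency between 8.2.1 and 8.3.3. It cannot be sized, because the share of patients on ICS alone or ICS with LAMA is not given.

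**What to change.** - In 8.7.1, remove the selection step from the main analysis. Keep one fixed set of the 8.3.3 baseline covariates in every PO2, PO3, SO1 and SO2 model, and report AIC-reduced models only as sensitivity analyses.
- Settle direct duplicates in advance rather than by AIC: use either FEV1 % predicted or GOLD stage, and either the Charlson score or its component diseases.
- Reconcile 8.2.1 with 8.3.3 by adding levels for ICS alone and for ICS with LAMA to the medication covariate, in both the PO1 tables and the models.

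The cost is a change of wording and at most slightly lower precision. In the simulations the SD was almost the same with and without selection.

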8.3.2. Exposure definitions

This is a binary comparison of COPD patients enrolled in the SLS and COPD patients in the CPRD. Hence the primary exposure of interest is whether a patient is enrolled in SLS (yes/no). A third grouping, COPD patients in Salford (who are not in SLS) will also be examined.

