8.5. Study size

The target sample size for the number of COPD patients enrolled in the SLS is 2,800. Study size in CPRD will be based on the prevalence of COPD diagnosis codes; this will be a minimum 2,800 to match but is expected to be considerably larger (x5-10).

WWEpi Project number: PRJ2282

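### The PO2/PO3 rule sets the SLS region's shrunken random effect against those of mostly smaller, more heavily shrunken CPRD regions, so its implied 5% false-flag rate is not held, clearly so for PO3

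*Protocol*

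**What the plan says.** Section 8.7.1 pools SLS and CPRD in a multilevel model: patient, practice, "local authority region (with SLS members being treated as a single distinct region"), then strategic health authority. After covariate selection, the protocol states: "We will then examine the random effect of the SLS region in the context of the random effects for the other regions". The decision follows: "if the random effect of the SLS region falls outside the 2.5-97.5 percentile range, we will conclude that SOC SLS behaves unusually", which is then taken as evidence of a Hawthorne effect. The rule carries over: "PO3 will be carried out using the same approach as for PO2", and SO1 and SO2 are handled in the same way.

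On size, section 8.5 says "The target sample size for the number of COPD patients enrolled in the SLS is 2,800", and for CPRD "this will be a minimum 2,800 to match but is expected to be considerably larger (x5-10"). Section 8.2 says that CPRD practices are about 10% of practices. Section 8.3.2 defines the exposure: "Hence the primary exposure of interest is whether a patient is enrolled in SLS (yes/no").

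The protocol does not give the number of local authorities, the between-region variance, an expected event rate or an error rate for the rule.

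**The concern.** A predicted random effect is not a raw regional rate. It is pulled towards zero, and the pull is stronger the less data the region holds. A percentile range built from small regions is therefore compressed, while a large region's prediction keeps nearly its full spread. If SLS is larger than most comparison regions, it can fall outside the range simply because it is better estimated, with nothing unusual about Salford.

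Two of the three co-primary objectives use this rule. A false flag would be reported as a Hawthorne effect in the SOC arm and would wrongly weaken confidence in extrapolating the trial.

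**Working it through.** **Formulae.** Let tau be the between-region SD on the log-rate scale and v_j the sampling variance of region j. The prediction has variance tau² × s_j, with s_j = tau²/(tau² + v_j). For an ordinary SLS region and equal-sized CPRD regions:

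P(flag) = 2 × [1 − Φ(1.96 × √(s_CPRD / s_SLS))]

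When all regions have the same size this is exactly 5%. That 5% is implied by the percentile limits; the protocol does not state it.

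**Inputs from the protocol.** SLS 2,800 enrolled, SOC arm analysed; CPRD 14,000-28,000 (5-10 times 2,800); 12 months of follow-up.

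**Assumptions.** SOC arm 1,400 (1:1 split; the allocation is not stated). 40-300 local authorities. tau 0.10-0.30. PO2 about 1.5 events a year with negative-binomial dispersion 1, so variance per patient is 1/1.5 + 1 = 1.667. PO3 at 4% a year (variance per patient 1/0.04 = 25) or 5% (1/0.05 = 20).

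**Region sizes.** CPRD regions average 1,400 patients only if there are 14,000/1,400 = 10 to 28,000/1,400 = 20 of them. At 40 regions, about the fewest for which a 2.5-97.5 percentile range means anything, they average 350-700. At 300 regions they average 47-93.

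**Worked example.** 14,000 patients in 150 regions (93 each), tau 0.15, tau² = 0.0225.

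| | v, CPRD region | s, CPRD | v, SLS | s, SLS | P(flag) |
|---|---|---|---|---|---|
| PO2 | 1.667/93 = 0.018 | 0.56 | 1.667/1,400 = 0.0012 | 0.95 | 13% |
| PO3 (4%) | 25/93 = 0.27 | 0.08 | 25/1,400 = 0.018 | 0.56 | 47% |

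**Range, closed form.**

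| CPRD patients | Regions | tau | PO2 | PO3 (5%) |
|---|---|---|---|---|
| 28,000 | 40 | 0.30 | 5.1% | 6.6% |
| 28,000 | 150 | 0.25 | 6.4% | 19% |
| 28,000 | 150 | 0.15 | 8.9% | 30% |
| 14,000 | 100 | 0.15 | 10.4% | 36% |
| 14,000 | 200 | 0.10 | 26% | 57% |
| 14,000 | 300 | 0.10 | 33% | 64% |

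Taking SLS as 2,800 raises these a little for PO2 and by more for PO3: the fourth row becomes 10.8% and 41%.

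**Simulation** with unequal region sizes, estimated tau and empirical percentiles gave 7-40% for PO2 and 13-59% for PO3. Not all of that excess is shrinkage. With equal-sized regions the empirical percentiles alone gave 7.9%, 7.1% and 5.8% for 50, 100 and 200 regions. At the mild end (tau 0.30, 28,000 patients, 40-100 regions), PO2 was 5-6% in closed form and 7-10% simulated.

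**Other reading of the range.** If it means ±1.96 tau of the fitted distribution, P(flag) = 2 × [1 − Φ(1.96/√s_SLS)]. In the worked example PO2 gives 1.96/√0.95 = 2.01, so 4.4%. PO3 gives 1.96/√0.56 = 2.62, so 0.9%. Over the grid this is about 3-5% for PO2 and 0-4% for PO3.

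**The case against.** The main objections, and what stands of each:

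- **The range is not fully defined.** The text does not say whether the percentiles are empirical or those of the fitted distribution, and an SAP could settle that. The preceding sentence points to the other regions' random effects, which is the plain reading. The ambiguity stands, but it does not rescue the rule: under the second reading a shrunken SLS value is set against an unshrunken range, and the error reverses.
- **The size is assumed.** This stands. A reader might infer that PO2 will be falsely flagged far more often than 5%. The documents do not support that: with 28,000 patients, 150 authorities and tau 0.25 the closed form gives only 6.4%. Only the direction follows from the protocol's own sizes, given more than about 20 regions.
- **An adjusted rate ratio is available anyway.** A reader might infer that the plan rules one out. It does not. Section 8.7.1 keeps an SLS indicator in the data set, and a region effect can be exponentiated. But the plan gives the indicator no part in the decision and specifies no ratio or interval for the exposure that section 8.3.2 calls primary.
- **Other evidence is planned.** Stratified descriptions, the before-and-after analysis in SO3 and the Greater Manchester CPRD comparison all temper the consequence. It would be wrong to say that nothing else bears on PO2. None of them corrects the stated decision rule.

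**Conclusion.** The rule is wrong as written, because its false-flag rate is driven by the size of the comparison regions and by the outcome's frequency. On the plain reading it exceeds the implied 5% whenever CPRD regions are on average smaller than SLS. For PO2 the excess runs from slight (about 5-10%, with large tau and few, large regions) to about 40% (small tau, many small regions). For PO3 it is well above 5% in nearly all settings, roughly 13-65%; the mildest closed-form case is about 7%. Part of the simulated excess comes from taking empirical percentiles from few regions. On the fitted-distribution reading the rule is too strict, and for PO3 it would rarely flag anything.

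These sizes rest on an assumed 1:1 split and on assumed region counts, tau and event rates. The case is firm for PO3; for PO2 the direction is firm and the size is open.

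**What to change.** In section 8.7.1:

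1. Enter the retained SLS indicator as a fixed effect in place of the SLS region's random effect. With both in the model, the fixed effect would absorb the regional one.
2. Estimate tau² from the CPRD regions only.
3. Report the adjusted SLS rate ratio with its 95% CI.
4. Call SLS unusual only if |beta_SLS| / √(tau² + SE²) > 1.96, which is a prediction interval for a new region.
5. Use the same rule for PO3, SO1 and SO2, and drop the comparison of predicted random effects as the decision rule.

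In scenarios where the protocol's rule flagged an ordinary region 8-31% (PO2) and 15-55% (PO3) of the time, a close variant of this rule gave about 4-7% and 4-9%. It is therefore near 5% but not exact for PO3. Ranking raw, unshrunk regional estimates is not a substitute: it errs the other way in most scenarios (mostly about 0-5%).

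The cost is wording and one model term, with the same data and software. The downside is that SLS will be flagged less often than under the percentile reading.

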8.7.2. Exploratory analysis

8.7.3. General considerations for data analyses

The main identified risks are:

- How linkable the SLS and CPRD datasets are e.g. can variables be extracted from both with the same (or very similar) definitions for all outcomes and potential confounders.
- Linkage of CPRD to HES and SES is not possible over the calendar dates that SLS
 has run as there is a lag time until these are released. Hence it may be necessary to
 restrict some analyses to data from earlier time periods.

8.8. Quality control

CPRD-GOLD has been used previously for descriptive drug utilization studies for prescription medications in respiratory diseases [16, 17, 18].

The standard operating procedures of University of Manchester will guide the conduct of the study, and will include internal quality audits; following rules for secure storage and backup of confidential data and study documentation; quality control procedures for programming, and requirements for senior scientific review.

The QC of analysis will be performed by GSK, in accordance with GSK Standard Operating Procedures (SOPs) and Guidance Documents, specifically the SOP_52213 (4.0): Conducting Quality Control Review of Worldwide Epidemiology Study Results . The common data model will allow the use of one set of programming following creation of a standardized structure. Wherever feasible, all statistical programming will be independently reviewed by a second analyst, with oversight by a senior statistician. Key study documents, such as the ISAC Protocol, statistical analysis plan, and study reports will undergo quality-control checks and review by the Scientific Steering Committee. Archiving of the project materials will be performed in accordance with GSK SOPs for documentation and archiving of observational studies.

